6.5.1. Subjects with Normal Renal Function (Cohort 1)

In general, subjects will abstain from all concomitant treatments (prescription or over-the-counter [OTC] medications) as described in the Exclusion Criteria section of the protocol, except for the treatment of AEs.

Limited use of nonprescription medications that are not believed to affect subject safety or the overall results of the study may be permitted on a case-by-case basis after approval by the sponsor or medical monitor.

6.5.2. Subjects with Impaired Renal Function (Cohort 2, Cohort 3 [if applicable] and Cohort 4 [if applicable])

Subjects are permitted to be on stable doses of background medications (including herbal supplements) if they are considered necessary for the welfare of the study subjects (i.e., standard therapy for the underlying disease), are not contraindicated with the study drug and are unlikely to interfere with the PK of the study drug. Whenever possible, attempts must be made to not alter the doses and regimens of the concomitant medications after Day 1 and until the end of study.

6.6. Intervention After the End of the Study

No interventions are planned after the end of the study.

7. Discontinuation of Study Intervention and Subject Discontinuation/Withdrawal

7.1. Discontinuation of Study Intervention

In rare instances, it may be necessary for a subject to permanently discontinue (definitive discontinuation) study intervention. If study intervention is definitively discontinued, the subject will remain in the study to be evaluated for AEs. See the Schedule of assessments (SoA) (Section 1.2) for data to be collected at the time of discontinuation of study intervention and follow-up and for any further evaluations that need to be completed.

As any new study drug may have unexpected AEs, the following potential toxicities for HM15912 should be considered while making a decision to put the study drug on temporary hold or permanently discontinue. The details on grading and management for these toxicities are provided in Appendix 5.

- cardiovascular toxicity
- rash/inflammatory dermatitis and other skin disorders
- liver toxicity
- gastrointestinal events

Other reasons for discontinuation of study drug include the following:

- subject request
- safety concern
- pregnancy
- lost to follow up
- death
- decision by sponsor or investigator
- protocol-specified criteria

7.2. Subject Discontinuation/Withdrawal from the Study

- A subject may withdraw from the study at any time at his/her own request, or may be withdrawn at any time at the discretion of the investigator for safety, behavioral, compliance, or administrative reasons. This is expected to be uncommon.
- At the time of discontinuing from the study, if possible, an early discontinuation visit should be conducted, as shown in the SoA (Section 1.2). See SoA (Section 1.2) for data to be collected at the time of study discontinuation and for any further evaluations that need to be completed.

- At the early discontinuation visit, every effort must be made to complete scheduled assessments. However, lack of completion of all or any of the early discontinuation/withdrawal procedures will not be viewed as protocol deviations so long as the subject's safety was preserved.
- The subject will be permanently discontinued both from the study intervention and from the study at that time.
- If the subject withdraws consent for disclosure of future information, the sponsor may retain and continue to use any data collected before such a withdrawal of consent.
- If a subject withdraws from the study, he/she may request destruction of any samples taken and not tested, and the investigator must document this in the site study records.

7.3. Study Subject Replacement

- For both Parts 1 and 2, subjects who withdraw from the study for non-safety related reasons and who are considered to be non-evaluable with respect to the primary objective may be replaced at the discretion of the sponsor but the maximum number of meaningfully evaluable patients will be not more than planned 8.

7.4. Lost to Follow up

A subject will be considered lost to follow-up if he or she repeatedly fails to return for scheduled visits and is unable to be contacted by the study site.

The following actions must be taken if a subject fails to return to the clinic for a required study visit:

- The site must attempt to contact the subject and reschedule the missed visit as soon as possible and counsel the subject on the importance of maintaining the assigned visit schedule and ascertain whether or not the subject wishes to and/or should continue in the study.
- Before a subject is deemed lost to follow up, the investigator or designee must make every effort to regain contact with the subject (where possible, 3 telephone calls and, if necessary, a certified letter to the subject's last known mailing address or local equivalent methods). These contact attempts should be documented in the subject's medical record.
- Should the subject continue to be unreachable, he/she will be considered to have withdrawn from the study.

Discontinuation of specific sites or of the study as a whole are handled as part of Appendix 1.

8. Study Assessments and Procedures

- Study procedures and their timing are summarized in the SoA (Section 1.2). Protocol waivers or exemptions are not allowed.
- Immediate safety concerns should be discussed with medical monitor or the sponsor immediately upon occurrence or awareness to determine if the subject should continue or discontinue study intervention.
- Adherence to the study design requirements, including those specified in the SoA (Section 1.2), is essential and required for study conduct.
- All screening evaluations must be completed and reviewed to confirm that potential subjects meet all eligibility criteria. The investigator will maintain a screening log to record details of all subjects screened and to confirm eligibility or record reasons for screening failure, as applicable.
- Procedures conducted as part of the subject's routine clinical management (e.g., blood count) and obtained before signing of the ICF may be utilized for screening or baseline purposes provided the procedures met the protocol-specified criteria and were performed within the time frame defined in the SoA (Section 1.2).
- The maximum amount of blood collected from each subject over the duration of the study will be in line with local regulations. Repeat or unscheduled samples may be taken for safety reasons or for technical issues with the samples.

8.1. Efficacy Assessments

Efficacy is not assessed in this study.

8.2. Safety Assessments

Planned time points for all safety assessments are provided in the SoA (Section 1.2). All clinically significant abnormalities from the safety assessments will be recorded as AEs.

8.2.1. Physical Examinations

- A full physical examination will include, at a minimum, assessments of general appearance Skin, Head, Ears, Eyes, Nose and throat, Cardiovascular, Respiratory, Gastrointestinal and Neurological, Lymph nodes, Extremities, Musculoskeletal and Psychiatric systems.
- A brief physical examination will include, at a minimum, assessments of the skin, respiratory, cardiovascular system, and abdomen (liver and spleen).
- Height, Weight and BMI will also be measured according to the SoA (Section 1.2). And BMI will be calculated using Height assessed at the screening.
- Investigators should pay special attention to clinical signs related to previous serious illnesses.

8.2.2. Vital Signs

- Tympanic body temperature, heart rate, respiratory rate, and blood pressure will be assessed.
- Blood pressure and heart rate will be measured after the subject has been lying down or sitting to rest for ≥ 5 minutes in a quiet setting without distractions. Blood pressure and heart rate will be measured at 2 consecutive times at least 2 minutes apart. Each measurement and the mean value will be recorded on the eCRF. Completely automated devices will be used. Manual techniques will be used only if an automated device is not available.

8.2.3. Electrocardiograms

- A 12 lead ECG will be obtained at scheduled timepoints in the SoA (Section 1.2) using an ECG machine that automatically calculates the HR and measures PR, QRS, QT, and QTc intervals. Additional ECGs will be performed for cause as needed to evaluate AEs.
- The 12-lead ECGs will be performed after the subject has been resting supine for ≥ 5 minutes.
- A triplicate 12-lead ECGs will be performed at screening period and Day1. At all other times, however, single 12-lead ECGs will be performed as outlined in the SoA (Section 1.2).
- Limited to Day 1, ECGs will be performed at predose and at 4 hours postdose, and a ± 30 -minute assessment window is allowed for measurement 4 hours postdose.
- The triplicate ECGs will be recorded at least 30 seconds apart from each other, not exceeding a time period of 3 minutes for the completion of all 3 ECGs.
- Investigator's assessment of clinical significance ('abnormal, not clinically significant' or 'abnormal, clinically significant') will be recorded in the eCRF. Centralized ECG vendor will be used for ECG measurement and independent reading.

8.2.4. Clinical Safety Laboratory Assessments

- See Appendix 2 for the list of clinical laboratory tests to be performed and to the SoA (Section 1.2) for the timing and frequency. Blood sample collection, processing, and shipping details will be outlined in a separate laboratory manual.
- The investigator must review the laboratory report, document this review, and record any clinically relevant changes occurring during the study in the AE section of the eCRF. The laboratory reports must be filed with the source documents. Clinically significant abnormal laboratory findings are those which are not associated with the underlying disease, unless judged by the investigator to be more severe than expected for the subject's condition.
- All laboratory tests with values considered clinically significantly abnormal during participation in the study or up to last follow-up visit should be repeated until the values

return to normal or baseline or are no longer considered clinically significant by the investigator or medical monitor.

- If such values do not return to normal/baseline within a period of time judged reasonable by the investigator, the etiology should be identified and the sponsor notified.
- All protocol-required laboratory assessments, as defined in Appendix 2, must be conducted in accordance with the laboratory manual and the SoA (Section 1.2).
- If laboratory values from non-protocol specified laboratory assessments performed at the institution's local laboratory require a change in subject management or are considered clinically significant by the investigator (e.g., SAE or AE), then the results must be recorded as narration in the eCRF.

8.2.5. Injection Site Assessment

Injection site assessments will be performed at the timepoints specified in the SoA (Section 1.2).

- After administration of study drug, the injection site will be marked with a pen. The local reaction from the injection site will be evaluated quantitatively using a Draize scale or similar scale. If an injection site reaction like pain on palpation, itching, erythema, edema, induration is observed, it must be recorded as an AE.
- Erythema will be evaluated as follows:
 - 0 – no erythema
 - 1 – very slight erythema (barely perceptible)
 - 2 – well-defined erythema
 - 3 – moderate-to-severe erythema
 - 4 – severe erythema (beet redness) to slight eschar formations (injuries in depth)
- Edema will be evaluated as follows:
 - 0 – no edema
 - 1 – very slight edema (barely perceptible)
 - 2 – slight edema (edges of area well defined by definite raising)
 - 3 – moderate edema (raised approximately 1 mm)
 - 4 – severe edema (raised more than 1 mm and extending beyond the area of exposure)
- For the irritation assessment, all irritation events will be documented as AEs. The diameter of the affected area will be measured with a paper measuring tape in centimeters and the condition of the injection site will be recorded. Digital photography will be used to document all positive injection site reactions.

- In case of clinically significant injection site reactions, subjects may undergo a dermatological consultation and/or cutaneous biopsies for further histological examination of the injection site reaction.

8.3. Adverse Events and Serious Adverse Events

AEs will be reported by the subject (or, when appropriate, by a caregiver, surrogate, or the subject's legally authorized representative).

The investigator and any qualified designees are responsible for detecting, documenting, and recording events that meet the definition of an AE or SAE and remain responsible for following up AEs that are serious, considered related to the study intervention or study procedures, or that caused the subject to discontinue the study (see Section 7).

8.3.1. Time Period and Frequency for Collecting AE and SAE Information

All AE and SAEs will be collected from the signing of the ICF until the last visit at the time points specified in the SoA (Section 1.2).

All SAEs will be recorded and reported to the sponsor or designee immediately and under no circumstance should this exceed 24 hours, as indicated in Appendix 3. The investigator will submit any updated SAE data to the sponsor within 24 hours of it being available.

Investigators are not obligated to actively seek AE or SAE after conclusion of the study participation. However, if the investigator learns of any SAE, including a death, at any time after a subject has been discharged from the study, and he/she considers the event to be reasonably related to the study drug or study participation, the investigator must promptly notify the sponsor.

8.3.2. Method of Detecting AEs and SAEs

The method of recording, evaluating, and assessing causality of AE and SAE and the procedures for completing and transmitting SAE reports are provided in Appendix 10.3.

Care will be taken not to introduce bias when detecting AEs and/or SAEs. Open-ended and non-leading verbal questioning of the subject is the preferred method to inquire about AE occurrences.

8.3.3. Follow-up of AEs and SAEs

After the initial AE/SAE report, the investigator is required to proactively follow each subject at subsequent visits/contacts. All SAEs, and AEs of special interest (as defined in Section 8.3.7), will be followed until resolution, stabilization, the event is otherwise explained, or the subject is lost to follow-up (as defined in Section 7.4). Further information on follow-up procedures is provided in Appendix 10.3.

The Investigator must record follow-up information. Follow-up information is reported in the eCRF as with initial AE/SAEs. Follow-up questions to Investigators regarding SAEs are queried directly to the Investigator.

Follow-up information must be reported according to the following:

- **SAEs:** All SAEs must be followed until the outcome of the events is “recovered/resolved”, “recovered/resolved with sequelae”, or “fatal”, and until all queries have been resolved. Cases of chronic conditions, cancer, or AEs ongoing at time of death (where death is due to another AE) may be closed with the outcome “recovering/resolving” or “not recovered/not resolved”. Cases can be closed with the outcome of “recovering/resolving” when the subject has completed the follow-up period and is expected by the Investigator to recover.

The SAE follow-up information should only include new (e.g., corrections or additional) information and must be reported **within 24 hours** of receipt of the information. This is also the case for previously non-serious AEs which subsequently become SAEs.

- **Non-serious AEs:** Non-serious AEs must be followed until the outcome of the event is “recovering/resolving”, “recovered/resolved”, or “recovered/resolved with sequelae” or until the end of the follow-up period stated in the protocol, whichever comes first, and until all queries related to these AEs have been resolved. Cases of chronic conditions, cancer, or AEs ongoing at time of death (where death is due to another AE) may be closed with the outcome of “recovering/resolving” or “not recovered/not resolved”. Cases can be closed with the outcome of “recovering/resolving” when subject has completed the follow-up period and is expected by the Investigator to recover.

If a potential hypersensitivity reaction is observed, additional blood samples may be required to further characterize the potential hypersensitivity reaction. If anaphylactic shock is suspected, blood samples may be taken for the measurement of tryptase. In this case, a blood sample should be taken 3 to 4 hours after the event and again approximately 1 to 2 weeks later to determine tryptase baseline levels. In addition, assessments for elevated histamine levels may be considered.

The Investigator must ensure that the worst-case severity and seriousness of an event is kept throughout the study, i.e., if the severity of an AE changes over time then it should be reported as a single AE with the most severity. A worsening of an unresolved AE must be reported as follow up with re-assessment of severity and/or seriousness of the event.

If an AE is resolved and reappears later then it should be reported as a new AE.

8.3.4. Regulatory Reporting Requirements for SAEs

- Prompt notification by the investigator to the sponsor of a SAE is essential so that legal obligations and ethical responsibilities towards the safety of subjects and the safety of a study drug under clinical investigation are met.
- The sponsor has a legal responsibility to notify both the local regulatory authority and other regulatory agencies about the safety of a study drug under clinical investigation. The sponsor will comply with country-specific regulatory requirements relating to

safety reporting to the regulatory authority, Institutional Review Boards (IRB)/Independent Ethics Committees (IEC), and investigators.

- For all studies except those utilizing medical devices investigator safety reports must be prepared for suspected unexpected serious adverse reactions (SUSAR) according to local regulatory requirements and sponsor policy and forwarded to investigators as necessary.
- An investigator who receives an investigator safety report describing a SAE or other specific safety information (e.g., summary or listing of SAEs) from the sponsor will review and then file it along with the Investigator's Brochure and will notify the IRB/IEC, if appropriate according to local requirements.

8.3.5. Pregnancy

- Details of all pregnancies in female subjects and, if indicated, female partners of male subjects will be collected after the start of study drug and until last follow-up visit. All subjects must be instructed to notify the Investigator immediately if she or his partner becomes pregnant or suspects to be pregnant during the study.
- If a pregnancy is reported, the investigator should inform the sponsor within 24 hours of learning of the pregnancy and should follow the procedures outlined in Appendix 10.4.
- Abnormal pregnancy outcomes (e.g., spontaneous abortion, fetal death, stillbirth, congenital anomalies, ectopic pregnancy) are considered SAEs and must be reported using the SAE form.

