Approximately 16 subjects will be enrolled in Part 1; 8 subjects with severe renal impairment (Cohort 2) and approximately 8 with normal renal function (Cohort 1). The 8 subjects of Cohort 2 will be recruited first. After the end of recruitment of Cohort 2, the demographics will be pooled to determine an average value for age and weight which will be used as a reference value for Cohort 1. The subjects with normal renal function in Cohort 1 will be recruited later such that each subject's age is within ± 10 years and weight is within ± 15 kg of the mean of the Cohort 2. An attempt will be made to maintain a similar male/female ratio between Cohort 1 and Cohort 2. Care will be taken when recruiting the subjects with normal renal function such that the entire group is not younger and of lower body weight than the impaired subjects.

Part 2 will be conducted if the point estimate of geometric mean ratio (GMR) of $AUC_{0-\infty}$ for the severe renal impairment group (Cohort 2) compared to the control group (Cohort 1) [REDACTED]. Based on whether the decision criterion to proceed to Part 2 is met, up to 8 subjects with moderate renal impairment (Cohort 3) and 8 subjects with mild renal impairment (Cohort 4), matched for demographic character to control group will be enrolled.

For both Parts 1 and 2, subjects who withdraw from the study for non-safety related reasons and who are considered to be non-evaluable with respect to the primary objective may be replaced at the discretion of the sponsor but the maximum number of meaningfully evaluable patients will be not more than planned 8.

Each subject will receive a single dose of either HM15912 administered SC in the abdomen on the Day 1. Blood samples will be collected from subjects to determine PK of HM15912 up to 29 days post-dose.

Subjects will be confined to the unit PK sampling and safety assessments (as specified in the Table 2). Inpatient period will be approximately 8 days, with admission to the Clinical Research Unit (CRU) on Day -1, dosing on Day 1 and discharge in the Day 8. After completion of study procedures on Day 2, if subjects request to discharge, they may be discharged from the CRU, on their desired date, at the discretion of Investigator. If subjects discharge earlier than Day 8 and based on the subject's request, Day 3, 4, 5, 6, and 7 procedures can be done in outpatient visit. These outpatient visit could be replaced to nurse home visit at the discretion of investigator.

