After the inpatient period, outpatient visits will take place on Day 10, 15, 22 and 29 for the collection of PK samples and safety assessments. On Day 10, if subjects request, outpatient visit could be replaced with nurse home visit upon the investigator's discretion. Day 29 follow up visit will mark the end of study visit.

Physical examinations, supine 12-lead electrocardiogram (ECG), vital sign measurements, and clinical laboratory tests will be conducted and AEs will be monitored throughout the study to assess safety.

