5.1.1. All Subjects

1. Subjects voluntarily agree to participate in this study and sign an IRB-approved informed consent prior to performing any of the Screening visit procedures.
2. Males and females ≥ 18 and ≤ 80 years of age at the Screening visit
3. Body mass index (BMI) of ≥ 17.5 to $\leq 40.0\text{kg}/\text{m}^2$
4. Female subjects must be non-pregnant and non-lactating and either surgically sterile (e.g., bilateral tubal occlusion, hysterectomy, bilateral salpingectomy, bilateral oophorectomy), or post-menopausal for ≥ 12 months. Postmenopausal status will be confirmed through testing of follicle-stimulating hormone (FSH) levels ≥ 40 IU/L at the Screening visit for amenorrheic female subjects ≤ 60 years of age.
5. Male subjects must be surgically sterile (at least 1-year post vasectomy), abstinent or if engaged in sexual relations with women of child-bearing potential, the subject and his partner must be using the following acceptable contraceptive methods from the Screening visit and for a period of 60 days after the dose of IP. Acceptable methods of contraception for males are the use of condoms together with spermicidal foam/gel/film/cream/suppository. Effective contraceptives for the female partner include: surgical sterilization (e.g., bilateral tubal occlusion, hysterectomy, bilateral salpingectomy, bilateral oophorectomy), hormonal contraception, intrauterine contraception/device or barrier methods (female condom, diaphragm, sponge, cervical cap) together with spermicidal foam/gel/film/cream/suppository. The adequacy of other methods of contraception will be assessed on a case-by-case basis by the Principal Investigator.

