- The investigator will attempt to collect pregnancy information on any male subject's female partner who becomes pregnant while the male subject is in this study. This applies only to male subjects who receive study drug.
- After obtaining the necessary signed informed consent from the pregnant female partner directly, the investigator will record pregnancy information on the appropriate form and submit it to the sponsor within 24 hours of learning of the partner's pregnancy. The female partner will also be followed to determine the outcome of the pregnancy. Information on the status of the mother and child will be forwarded to the sponsor. Generally, the follow-up will be no longer than 6 to 8 weeks following the estimated delivery date. Any termination of the pregnancy will be reported regardless of fetal status (presence or absence of anomalies) or indication for the procedure.

Female Subjects who become pregnant

- The investigator will collect pregnancy information on any female subject who becomes pregnant while participating in this study. The initial information will be recorded on the appropriate form and submitted to the sponsor within 24 hours of learning of a subject's pregnancy.
- The subject will be followed to determine the outcome of the pregnancy. The investigator will collect follow-up information on the subject and the neonate and the information will be forwarded to the sponsor. Generally, follow-up will not be required for longer than 6 to 8 weeks beyond the estimated delivery date. Any termination of pregnancy will be reported, regardless of fetal status (presence or absence of anomalies) or indication for the procedure.
- While pregnancy itself is not considered to be an AE or SAE unless there is a suspicion that the study drug may have interfered with the effectiveness of a contraceptive medication, any pregnancy complication or elective termination of a pregnancy for medical reasons will be reported as an AE or SAE.
- A spontaneous abortion (occurring at <22 weeks gestational age) or still birth (occurring at >22 weeks gestational age) is always considered to be an SAE and will be reported as such.

- Any post-study pregnancy related SAE considered reasonably related to the study drug by the investigator will be reported to the sponsor as described in Section 8.3.4. While the investigator is not obligated to actively seek this information in former study subjects, he or she may learn of an SAE through spontaneous reporting.

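### Reporting and collection of partner pregnancies end at Day 29, while the protocol's contraception requirement for male subjects runs to 60 days after the dose

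*Protocol*

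**What the plan says.** Four parts of the protocol bear on this point.

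- **Contraception.** Section 5.1.1, item 5 (repeated in the Synopsis) applies to male subjects who are not sterile or abstinent and have a partner of childbearing potential. The subject and his partner must use "acceptable contraceptive methods from the Screening visit and for a period of 60 days after the dose of IP".
- **Collection and notification.** Section 8.3.5 covers pregnancies in female subjects and, with an if-indicated qualifier, those in partners: details in "female partners of male subjects will be collected after the start of study drug and until last follow-up visit". Subjects must tell the investigator at once "if she or his partner becomes pregnant or suspects to be pregnant during the study".
- **Appendix 4 (Section 10.4).** The investigator tries to obtain information on a partner "who becomes pregnant while the male subject is in this study". A pregnancy that is picked up is followed to its outcome.
- **End of study.** Section 4.1 gives "dosing on Day 1 and discharge in the Day 8", and then "Day 29 follow up visit will mark the end of study visit".

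After the study, Section 8.3.1 requires the investigator to pass on an SAE that he or she happens to learn of and considers related. Appendix 4 adds: "Any post-study pregnancy related SAE considered reasonably related to the study drug by the investigator will be reported to the sponsor". Neither section obliges the investigator to look for such events. The Schedule of Assessments has no contact after Day 29.

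**The concern.** Female subjects must be surgically sterile or postmenopausal (Section 5.1.1, item 4), so partners of male subjects are the main route by which a pregnancy could arise in this study. Men are expected in the cohorts: Section 5.1.2 says that no cohort may consist of one sex only.

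For these couples the protocol restricts conception for 60 days after the dose but stops asking about it less than halfway through. A partner conception on Day 35, for example, falls inside the contraception period, yet the subject has no duty to report it and the site has no instruction to record it. The follow-up to outcome in Appendix 4 would then never start. Any later statement about partner pregnancies could speak only for the first 28 post-dose days.

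**Working it through.** **Inputs**

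- Dose: Day 1 (Protocol 4.1).
- Last visit: Day 29, window ±1 day (Table 1); nominal PK time 672 h (Table 2).
- Contraception period: to 60 days after the dose (Protocol 5.1.1).
- Screening: up to 28 days; total duration per subject: up to about 57 days (Synopsis, Duration of Treatment).

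**Check of the calendar.** The plan's own total reproduces: 28 screening days + 29 study days = 57 days. The PK table agrees on the time from the dose: 672 h / 24 = 28 days.

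**Uncovered post-dose days.** Uncovered = 60 − (day of last visit − 1).

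| Last visit | Days after dose | Uncovered days | Share of 60 |
|---|---|---|---|
| Day 28 | 27 | 33 | 55.0% |
| Day 29 (nominal) | 28 | 32 | 53.3% |
| Day 30 | 29 | 31 | 51.7% |

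At the nominal visit the uncovered stretch is Day 30 to Day 61. More than half of the post-dose period is uncovered on every permitted visit date, and a subject who withdraws early leaves a longer gap. The denominator is post-dose days. If the full 28 screening days were added to the contraception period, the share would be 32 / (28 + 60) = 36%, but those days precede any exposure.

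**Does another provision close the gap?** Set side by side:

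- Section 8.3.5, collection: ends at the last visit.
- Section 8.3.5, duty to notify: pregnancies during the study.
- Appendix 4, partners: pregnancies arising while the man is in the study.
- Section 8.3.1 and Appendix 4, post-study: SAEs judged related, if the investigator learns of them. The Appendix 4 sentence stands in the list for female subjects. The same list says that pregnancy itself is normally neither an AE nor an SAE.

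None of these reaches an uncomplicated partner pregnancy conceived after Day 29.

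**Conceived before Day 29, learned of later.** Appendix 4 turns on when the partner becomes pregnant, which would include this case. The first sentence of Section 8.3.5 ends collection at the visit, which would exclude it. The text does not say which governs.

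**The case against.** The best answer is that a contraception requirement and a pregnancy-collection window serve different purposes and need not have the same length. That is correct as far as it goes. Section 5.1.1 is an eligibility criterion. A reader might infer that it defines a 60-day period of reproductive risk which Section 8.3.5 then contradicts, but the protocol never calls it that, and no passage says the two periods must match. What stands is narrower: the protocol gives no reason for ending collection before the restriction on conception ends.

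A reader might also infer that every conception shortly before Day 29 is lost because it would not yet be known. Appendix 4 does not support that. Nor does the rule in Section 8.3.5 that the sponsor be informed within 24 hours of learning of a pregnancy, since it carries no end date. The fair statement is that the text is unclear.

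A third tempting inference is that much drug remains at Day 29 in impaired subjects. The documents give no half-life for that group. The mean half-lives in the first-in-human study (Section 2.2) were 108 to 167.4 h. On a first-order calculation 672 h is then 6.2 to 4.0 half-lives, with about 1.3% to 6% remaining. The 2.5-fold figure in Section 4.3 is a margin for exposure, not a forecast of half-life, and the nephrectomized-rat study showed no effect on PK. The point therefore does not rest on residual drug.

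Finally, numbers are small (up to about 32 subjects), contraception is mandated, and the safety endpoints do not include partner pregnancy. All of this limits the weight of the point without closing the gap.

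**Conclusion.** The concern holds as a mismatch between windows, not as an outright contradiction. Under the plan as written, 32 of the 60 post-dose days of the contraception period (53%; 52% to 55% over the visit window) carry no duty to report a partner pregnancy and no collection. Only a passive route for related SAEs remains. In addition, Section 8.3.5 and Appendix 4 leave open how to treat a conception before Day 29 that becomes known later.

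This rests on reading the last follow-up visit as Day 29, which Section 4.1 supports. It also assumes that nothing in the consent form or in the three protocol clarification letters named in the SAP Introduction, none of which could be seen, extends the reporting duty. The primary PK comparison is unaffected and few events are expected. It ranks as a cheap improvement to safety follow-up.

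**What to change.** Reconcile Section 5.1.1 (with the Synopsis), Section 8.3.5 and Appendix 4 as follows:

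1. The window for reporting and collecting partner pregnancies ends with the contraception period, whatever length the sponsor retains. This review takes no position on that length.
2. Conceptions within that window are collected whenever they become known, including after the last visit.
3. At Day 29, or at an early discontinuation visit, male subjects are told to report partner pregnancies through the end of the window.

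No SAE contact limited to men with partners of childbearing potential should be added. It would make SAE ascertainment unequal across subjects and cohorts in an open-label safety comparison.

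The cost is a protocol wording amendment with IRB/IEC approval, including a line in the Schedule of Assessments for the Day 29 instruction, and a slightly later close for this item only: about 32 days after the last subject's Day 29 visit if the present contraception period is kept (60 − 28). No extra visit or sample is needed.
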